In addition, HDAC has been well-recognized as potential targets for the treatment of numerous aging-related disorders (9) such as cancer (10). Therefore, we plan to evaluate the potential role of biomarkers of aging with the combination of HCQ plus VOR.

These findings support a phase II study VOR/HCQ versus standard therapy RGF in patients failing standard therapies.

We hypothesize that VOR/HCQ will have improved efficacy when compared to RGF in treatment-refractory mCRC patients. This hypothesis is based on the observations that:

1. In refractory mCRC patients, the role of continued VEGF inhibition in mCRC has not been established (4).
2. Only a modest improvement in survival was reported with the use of RGF, an oral multi-kinase inhibitor with predominantly angiogenic inhibition, for mCRC patients who have failed standard therapies (3).
3. Autophagy inhibition enhances vorinostat-induced apoptosis via ubiquitinated protein accumulation in CRC models pre-clinically (5).
4. Clinical activity based on treatment-refractory mCRC patients enrolled in phase I (6) and the ongoing single arm Phase II study of VOR with HCQ therapy suggests a median PFS of > 3 months.

Our overall objective is to answer these questions: will VOR/HCQ be more efficacious than RGF, will VOR/HCQ be safe, and can biomarkers be identified that will predict clinical efficacy of VOR/HCQ and RGF in refractory mCRC patients?

Primary Objective(s):

- To determine the clinical efficacy with progression-free survival (PFS-1) of the combination of VOR plus HCQ when compared to RGF in treatment-refractory mCRC.

Secondary Objective(s):

- To determine the overall survival in refractory mCRC patients receiving VOR plus HCQ when compared to RGF.
- To determine the progression-free survival (PFS-2) of the crossover treatment, which is optional.
- To evaluate the tumor response rate in refractory mCRC patients receiving VOR plus HCQ when compared to RGF.
- To further define the safety of the combination of VOR/HCQ when compared to RGF in treatment-refractory mCRC.
- To identify biomarkers of autophagy and anti-angiogenic inhibition that are associated with clinical efficacy of VOR/HCQ and RGF, respectively, in mCRC.

Primary Endpoint(s):

- PFS-1: measured from the start of the first treatment the patient is randomized to until the date the criteria for progression are met or the date the patient is taken off study for any reason, whichever is shorter.

[figure not shown]
Secondary Endpoint(s):

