Autophagosomes fuse with lysosomes, which results in the proteolytic degradation of their contents. In eukaryotic cells, autophagy plays an important role in the disposal of damaged organelles and proteins and serves to generate alternative sources of energy for cell survival during cellular stress through the catabolization of protein substrates (32). The activation of stress response genes such as p53 by anticancer therapies can stimulate autophagy in addition to apoptosis (33). *Although prolonged autophagy can result in cancer cell death, recent investigations suggest that therapy-induced autophagy is a reversible response that promotes cancer cell survival and thus, may diminish the efficacy of some therapeutic agents (34-36).*

Therefore, autophagy may significantly contribute to resistance to a number of anticancer therapeutic modalities.

2.3.1 Autophagy as a mechanism of resistance to anti-cancer therapeutics.

The induction of autophagy has been observed in malignant cells after treatments, such as tamoxifen, imatinib, arsenic trioxide, histone deacetylase (HDAC) inhibitors, and rapamycin (3741). Histone deacetylase inhibitors, such as Vorinostat (VOR), have shown selective anti-cancer activity in preclinical and clinical models (10). The main effect of vorinostat, VOR, is inhibition of histone deacetylase (HDAC) activity, which causes hyperacetylation of all core histone proteins, H2A, H2B, H3 and H4. Hypoacetylation of histones is associated with condensed chromatin structure, which results in the repression of the transcription of many genes including those implicated in the regulation of cell survival, proliferation, differentiation and apoptosis. Through HDAC inhibition, vorinostat can restore the expression of silenced genes by remodeling the tightly coiled chromatin, leading to the subsequent induction of differentiation and apoptosis (42). VOR induces cell cycle arrest in either the G1 or G2M phases, downregulates cyclin D1 and D2, upregulates p53, p21 and p27 expression, and stimulates apoptosis.

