4.0 Inclusion and Exclusion Criteria Inclusion

Criteria:

1. Patients 18 years of age or older with histological documentation of metastatic colorectal cancer (mCRC).
2. ECOG performance status of 0-2.

3. Radiographical documentation of metastatic disease with imaging up to 6 weeks prior to enrollment.
4. Patients with mCRC must have been previously treated with irinotecan and/or oxaliplatin and/or VEGF/EGFR therapy or intolerant to these agents
5. Documentation of K-Ras mutational status
6. Adequate hematologic, renal and liver function (i.e. absolute neutrophil count $> 1000/\text{mm}^3$, platelets $> 75,000/\text{mm}^3$); creatinine < 2 times the upper limits of normal (ULN) total bilirubin $< 1.5 \text{ mg/dl}$, ALT and AST < 3 times above the ULN, ALT and AST can be < 5 times ULN if patients have hepatic involvement.
7. Able to provide written informed consent.
8. Patients with the potential for pregnancy or impregnating their partner must agree to follow acceptable birth control methods to avoid conception. Women of childbearing potential must have a negative pregnancy test within 72 hours prior to receiving the investigational product.
9. Tumor blocks available from previous surgery/biopsy, or if not available, patients willing to have biopsy.

Exclusion Criteria:

1. Patients receiving prior therapy with RGF, VOR, and/or HCQ.
2. Patients with uncontrolled brain metastases. Patients with brain metastases must be asymptomatic and off corticosteroids for at least one week.
3. Due to risk of disease exacerbation, patients with porphyria are not eligible.
4. Due to risk of disease exacerbation, patients with psoriasis are ineligible unless the disease is well controlled, and they are under the care of a specialist for the disorder who agrees to monitor the patient for exacerbations.
5. Patients with previously documented macular degeneration or untreated diabetic retinopathy (stable retinopathy is allowed).
6. Patients who have had chemotherapy or radiotherapy within 2 weeks (6 weeks for nitrosoureas or mitomycin C) prior to entering the study. For investigational targeted therapies, patients will need to clear for 5 half-lives (not applicable to standard of care therapies).
7. Patients may not be receiving any other investigational agents.
8. Patients should not have taken valproic acid or another histone deacetylase inhibitor for at least 2 weeks prior to enrollment.

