5.3 Treatment Requirements

All eligible patients who consent to this study must have a baseline evaluation (CT or MRI) within 6 weeks of the start of treatment.

Patient must meet all eligibility requirements to be entered onto the protocol.

5.3.1 Duration of Intervention and Evaluation:

Follow-up: A repeat CT scan will be performed after 2 cycles of treatment regimen to evaluate response based on RECIST 1.1 criteria (See Appendix 13.1 for definitions of response) (73). CT scans will be repeated at least every 2 cycles, or 8 weeks, to ensure no progression of disease. Patients will continue on VOR/HCQ or RGF until disease progression, unacceptable toxicity, withdrawal of consent by the patient, or decision of physician for patient's best interest. Crossover to the other arm will be allowed, but OPTIONAL, and will be determined by the treating physician for the patient's best interest. If patient is not given crossover treatment, then the patient will be off study and will be allowed to receive subsequent treatments. Each patient

will be followed for 1 year. We will follow the last patient for 12 months, at which time, the study will be completed for data analysis.

Interim analysis: The O'Brien-Fleming procedure will be used to conduct an interim analyses for efficacy when 50% of the patients complete the study. A statistical basis for stopping the study at the first look will be achieved if the test statistic indicates benefit in the VOR/HCQ Arm and exceeds 2.96259, corresponding to a significance level of 0.003. If the test statistic does not exceed 2.96259 at the first look then the trial will proceed to the final analysis. A treatment effect will be declared significant and beneficial at the final analysis if the test statistic indicates benefit and exceeds 1.96857, corresponding to a significance level of 0.047.

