Anti-convulsants: Because HCQ has known effects on P450 enzymes, patients requiring anticonvulsants may be treated with any of the non-enzyme inducing anti-convulsants, which include: felbamate, valproate acid, gabapentin, lamotrigine, tiagabine, topiramate, zonisamide, or levetiracetam. Patients requiring the use of enzyme-inducing anti-epileptic medication (phenytoin, carbamazepine, phenobarbital, primidone or oxcarbazepine) are not eligible for entry into the study. If these agents are required during the study, patients will discontinue study treatment.

Growth factors: Patients are allowed to continue hematological growth factors such as Aranesp if initiated before the protocol. G-CSF or GM-CSF will not be allowed as prevention in cycle 1, but could be used as needed for treatment of grade 4 or complicated neutropenia on cycle 1 or beyond. If prophylaxis is considered necessary by the clinical investigator beyond cycle 1, this is allowed.

Given the possibility of metabolic interaction through the P450 2D6 enzyme the concomitant administration of HCQ with digoxin, B blockers, cyclosporine and cimetidine should be closely monitored.

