10.0 Statistical Section

Analytic plan for primary objective:

mPFS-1: Historically, the mPFS for previously treated mCRC patients treated with RGF is 1.9 mos. We predict VOR/HCQ will improve mPFS to 3.8 months. We expect 5% lost to followup. Assuming a 36-month accrual period with 1 year for follow up, 36 subjects per group are necessary to obtain 80% power. With 5% lost to follow-up the sample size required per group is 38 ($=36/0.95$), therefore, the total required sample size is 76 subjects. As a result, the target accrual rate is 3-4 patients/month to achieve a target accrual at 36 months with an additional 12month follow-up.

Treatments will be contrasted with regard to PFS-1 with a proportional hazards model with adjustment for age, sex, race, and the baseline tumor K-RAS status (mutated, wild type); the adjusted hazard ratio, its 95% confidence interval, and the p-value for testing the null hypothesis that the log hazard ratio is zero will be presented. Survival curves will be illustrated with Kaplan-Meier plots. Interactions between treatment and baseline covariates will be explored.

If a patient does not complete Cycle 1 and is off study, then this patient will not be evaluable for efficacy but will be evaluable for toxicity.

Interim analysis: The O'Brien-Fleming procedure will be used to conduct an interim analyses for efficacy when 50% of the patients complete the study. A statistical basis for stopping the study at the first look will be achieved if the test statistic indicates benefit in the VOR/HCQ Arm and exceeds 2.96259, corresponding to a significance level of 0.003. If the test statistic does not exceed 2.96259 at the first look then the trial will proceed to the final analysis. A treatment effect will be declared significant and beneficial at the final analysis if the test statistic indicates benefit and exceeds 1.96857, corresponding to a significance level of 0.047. If a treatment effect is not declared at the interim analysis, a statistical basis for stopping the study for futility will be attained if the conditional power is less than or equal to 20%.

Analytic plan for secondary objectives:

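### Section 5.3.4 permits valproate on study on P450 grounds alone, although exclusion 8 classes it as an HDAC inhibitor, like vorinostat, and requires 2 weeks off it prior to enrollment

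*Combined protocol and SAP*

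**What the plan says.** Three parts of the combined protocol and SAP bear on this.

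- **On-study permission.** The anticonvulsant paragraph of Section 5.3.4 reads: "Because HCQ has known effects on P450 enzymes, patients requiring anticonvulsants may be treated with any of the non-enzyme inducing anti-convulsants". The drugs it names are "felbamate, valproate acid, gabapentin, lamotrigine, tiagabine, topiramate, zonisamide, or levetiracetam". It then lists five enzyme-inducing agents that make a patient ineligible and adds: "If these agents are required during the study, patients will discontinue study treatment". That stopping rule covers the enzyme inducers only.
- **Entry rule.** Exclusion 8 in Section 4.0 states: "Patients should not have taken valproic acid or another histone deacetylase inhibitor for at least 2 weeks prior to enrollment". The Synopsis carries the same criterion, and Section 6.0 repeats it in a footnote to the baseline medication review.
- **Class of the study drug.** Section 2.3.1 says: "The main effect of vorinostat, VOR, is inhibition of histone deacetylase (HDAC) activity". Section 5.6.2 also describes vorinostat as an HDAC inhibitor.

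**The concern.** The entry rule and the on-study list judge the same drug by different properties. Exclusion 8 looks at its HDAC activity; Section 5.3.4 looks only at enzyme induction. A patient could stop valproate for 2 weeks, enroll, be assigned to VOR/HCQ and resume it, or could start it for the first time on study. A patient who took it during regorafenib (RGF) could cross over to VOR/HCQ without a further check.

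What is at stake is whether the tested regimen contains one HDAC inhibitor. A patient taking both drugs would be analysed as VOR/HCQ while receiving two agents of that class. The Synopsis treats CDKN1A as a biomarker of VOR, and Section 10.0 relates biomarkers to PFS-1. It is a reasonable inference, not a documented effect, that a second drug of the class would make biomarker results and toxicity attribution harder to read in that patient.

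**Working it through.** No test, power or sample-size formula applies, and the plan states no figure on this point to reproduce. The check sets the texts side by side.

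1. **Is valproate permitted on study?** Yes, by name in Section 5.3.4. The list spells it valproate acid; I take this to be the valproic acid of exclusion 8. The permission also covers any non-enzyme-inducing anticonvulsant, so deleting the name alone would not bar the drug.
2. **On what ground?** P450 enzymes and HCQ only. The paragraph does not mention HDAC inhibition.
3. **Does the protocol itself class valproic acid as an HDAC inhibitor?** Yes. Exclusion 8 refers to valproic acid or *another* drug of that class, so no outside source is needed.
4. **Is vorinostat in that class?** Yes, by Sections 2.3.1 and 5.6.2.
5. **Does any other current rule bar the combination?** None was found.
   - Exclusion 7 concerns other investigational agents, and nothing makes valproate investigational.
   - The vorinostat interaction text in Section 5.6.2 covers CYP450 and coumarin anticoagulants, not other HDAC inhibitors.
   - The Section 6.0 footnote is attached to the baseline review only.
6. **Is exclusion 8 applied again before crossover?** No. The Section 6.0 eye-exam footnote does extend its rule to patients who cross over to VOR/HCQ, so re-checking at crossover has a precedent that was not extended to valproate.
7. **Can the situation arise?** Yes, though probably rarely. Exclusion 2 admits patients with asymptomatic brain metastases who are off corticosteroids, and Section 5.6.1 lists seizure among potential HCQ toxicities. The documents give no frequency of anticonvulsant use.

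**Size.** Planned enrollment is 38 per arm and 76 in total (Section 5.1).

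- One affected patient as a share of an arm: 1/38 = 2.6%.
- One affected patient as a share of the trial: 1/76 = 1.3%.
- Named anticonvulsants left if valproate is removed: 8 − 1 = 7.

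The percentages are the weight of one patient, not an estimate of how many there will be. For PFS-2 no share can be given, because crossover is optional and the number crossing over is not stated.

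**The case against.** The strongest reply is that nothing is inconsistent. Exclusion 8 is a washout before enrollment. The documents do not state its purpose, and it may be meant only to clear prior exposure. Section 5.3.4 governs a later period. The affected group is small, and no harm to efficacy or safety is shown.

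All of that stands, and it limits the weight of the point. It does not remove it: on either reading of the washout, Section 5.3.4 expressly allows valproate beside vorinostat without considering that both are HDAC inhibitors.

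A reader might draw stronger conclusions that the documents do not support:

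- **That the two rules contradict each other.** They apply at different times.
- **That PFS or safety results would be biased.** The documents contain no evidence of an effect of valproate with either regimen and no count of users.
- **That valproate should be barred in the RGF arm too.** Section 5.3.4 states no arm restriction, so use with RGF appears possible. But Section 5.6.3 describes RGF as a kinase inhibitor, so there is no duplication of class during RGF, and a check before crossover deals with later vorinostat exposure.
- **That unavoidable valproate should force a stop of VOR/HCQ, as for enzyme inducers.** This is out of proportion to an effect that is not shown. The protocol has lighter models: Section 5.3.4 asks that aprepitant be avoided and recorded if needed, and Section 5.4.2.2 lets HCQ continue when vorinostat is interrupted. A full stop would also reach the endpoint. Section 5.3.1 says: "If patient is not given crossover treatment, then the patient will be off study"; PFS-1 can end at "the date the patient is taken off study for any reason, whichever is shorter"; and Section 10.0 adds: "If a patient does not complete Cycle 1 and is off study, then this patient will not be evaluable for efficacy". Avoiding that would need a PFS-1 exception for one rare trigger, so that similar stops were handled differently. Interrupting vorinostat alone leaves the patient on study and needs no exception.

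**Conclusion.** The point holds as a cheap improvement, not as an error that threatens the trial. The protocol expressly permits a drug that it elsewhere classes as an HDAC inhibitor, and nothing prevents its use together with vorinostat, either in first-assigned VOR/HCQ patients or after crossover. The likely number of patients is small; each weighs 2.6% of a planned arm. Sample size, power and the analysis model are untouched.

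The conclusion rests on the protocol's own classification in exclusion 8, on the two spellings meaning the same drug, and on no other current text restricting the combination. It does not rest on any assumed effect of valproate on outcome.

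**What to change.** In Section 5.3.4:

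- Delete valproate from the permitted list.
- State that valproic acid and other non-study HDAC inhibitors are not to be used while the patient is receiving vorinostat.
- State that if valproate is clinically unavoidable, it is recorded and vorinostat is interrupted while it is given, with HCQ continuing as Section 5.4.2.2 already provides.

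In the crossover instructions, apply the exclusion 8 check (2 weeks off) before a patient starts VOR/HCQ as second regimen.

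**Cost.** One drug name is deleted, two sentences are added, and one check is made at crossover. Section 6.0 already schedules medication review at baseline, every cycle and off treatment, so detecting use needs no new visit. The downsides are one fewer anticonvulsant option, a possible vorinostat interruption in a rare patient (who would be on HCQ alone meanwhile), and a possible 2-week delay to crossover for a patient taking valproate at that point.

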5.4 Dose Modification for Toxicity

Toxicity Criteria - This study will utilize the CTCAE version 4.0 for toxicity and Adverse Event Reporting. A copy of the CTCAE version 4.0 can be downloaded from the CTEP home page (<http://ctep.cancer.gov>). All appropriate treatment areas will have access to a copy of the CTCAE version 4.0.

5.4.1 Major Events

Major Events are non-treatment-related grade 3 and 4 hematologic and non-hematologic toxicities. Treatment should be delayed for major events if the study drug may further complicate the non-treatment related event. If a major event requires a delay of treatment, treatment must be delayed until toxicity is resolved (\leq Grade 2 or \leq Baseline). If toxicity is not resolved in \leq 2 weeks, patient will be taken off treatment except if the patient experiences clinical benefit.

5.4.2 Dose Reduction for VOR and/or HCQ (see Table 2)

Dose can be decreased due to toxicity if deemed by the clinical investigator to be related to VOR. The dose reductions will be 300 mg (level -1), 200 mg (level -2).

Dose can be decreased due to toxicity if deemed by the clinical investigator to be related to HCQ. The dose reductions will be 400 mg (level -1), 200 mg (level -2).

If toxicity is thought to be due to VOR and HCQ, then dose reductions can be done for each drug as above.

5.4.2.1 HCQ Dose Modification

reinstitution of treatment can occur but at a reduced dose as described in Table 2.

If the AE recurs at the reduced dose, treatment will be held until the AE has resolved to \leq grade 1 and when resolved treatment can be reinstated at the next lower dose level. No more than 2 dose reductions are allowed during the maintenance cycles.

With particular regard to visual field deficits patients should be cautioned to report any visual symptoms, particularly difficulty seeing entire words or faces, intolerance to glare, decreased night vision, or loss of peripheral vision. **These symptoms of peripheral retinal toxicity should prompt drug discontinuation and ophthalmologic evaluation.**

5.4.2.2 VOR Dose Modification

Known VOR hematological or non-hematological toxicities will not be attributed to HCQ and will only be attributed to VOR and may result in VOR dose modifications. Toxicities having an attribution to VOR of possible, probable or definite will result in the following VOR dose modifications:

VOR administration will be delayed, reduced or discontinued based on weekly assessment of according to hematological and non-hematological toxicity criteria, as specified below.

If the administration of VOR has to be interrupted, the treatment with HCQ will proceed normally and no catch-up days of VOR. The total number of days of VOR administration and total dose of VOR will be recorded in the CRF.

5.4.3 Dose Modification for RGF (Table 3)

The starting dose will be RGF 160 mg PO daily, for 3 weeks, of a 4-week cycle, as determined by the phase III study in mCRC patients (3).

Dose can be decreased due to toxicity if deemed by the clinical investigator to be related to RGF. The dose reductions will be 120 mg (level -1), 80 mg (level -2).

Due to known hepatic toxicity, we will monitor liver function tests (ALT, AST and bilirubin) before initiation of RGF and monitor at least every two weeks during the first 2 months of treatment. Thereafter, monitor every cycle or more frequently as clinically indicated. Monitor liver function tests weekly in patients experiencing elevated liver function tests until improvement to less than 3 times the ULN or baseline. Temporarily hold and then reduce or permanently discontinue RGF depending on the severity and persistence of hepatotoxicity as manifested by elevated liver function tests or hepatocellular necrosis. See below for specific recommendations:

Interrupt Regorafenib for the following:

- NCI CTCAE Grade 2 hand-foot skin reaction (HFSR) [palmar-plantar erythrodysesthesia (PPE)] that is recurrent or does not improve within 7 days despite dose reduction; interrupt therapy for a minimum of 7 days for Grade 3 HFSR
- Symptomatic Grade 2 hypertension
- Any NCI CTCAE Grade 3 or 4 adverse reaction

Reduce the dose of Regorafenib to 120 mg:

- For the first occurrence of Grade 2 HFSR of any duration
- After recovery of any Grade 3 or 4 adverse reaction
- For Grade 3 aspartate aminotransferase (AST)/alanine aminotransferase (ALT) elevation; only resume if the potential benefit outweighs the risk of hepatotoxicity

Reduce the dose of Regorafenib to 80 mg:

- For re-occurrence of Grade 2 HFSR at the 120 mg dose
- After recovery of any Grade 3 or 4 adverse reaction at the 120 mg dose (except hepatotoxicity)

Discontinue Regorafenib permanently for the following:

- Failure to tolerate 80 mg dose
- Any occurrence of AST or ALT more than 20 times the upper limit of normal (ULN)
- Any occurrence of AST or ALT more than 3 times ULN with concurrent bilirubin more than 2 times ULN
- Re-occurrence of AST or ALT more than 5 times ULN despite dose reduction to 120 mg

- For any Grade 4 adverse reaction; only resume if the potential benefit outweighs the risks

